Participants may not have received an investigational drug within 30 days (including investigational drugs for prophylaxis of COVID-19) or used an invasive investigational medical device within 30 days or received investigational Ig or investigational monoclonal antibodies within 3 months, or received convalescent serum for COVID-19 treatment within 4 months or received an investigational vaccine (including investigational Adenoviral-vectored vaccines) within 6 months before the planned administration of the 1st dose of the Janssen Ad26.CoV2.S vaccine. During the study, the use of investigational vaccines, drugs or devices is not allowed. Treatment with investigational COVID-19 drugs after diagnosis of a COVID-19 case is allowed during the follow-up period and needs to be recorded in the COVID-19 episode description.

Licensed live attenuated vaccines should be given at least 28 days before or at least 28 days after a study vaccination. Other licensed (not live) vaccines (e.g., influenza, tetanus, hepatitis A, hepatitis B, rabies) should be given more than 14 days before (or more than 14 days after, as per Exclusion

Criteria) administration of any dose of the Janssen Ad26.CoV2.S vaccine in order to avoid potential confusion of adverse reactions and potential immune interference. If a vaccine is indicated in a postexposure setting (e.g., rabies or tetanus), it must take priority over the Janssen Ad26.CoV2.S vaccine. Receipt of any COVID-19 vaccine (outside the study) at any timepoint during the study must be recorded. The name and date(s) of administration of the COVID-19 vaccine should be recorded in the eCRF.

Subjects should not receive any pre-exposure prophylactic medications for COVID-19 until after completion of the Day 28 Visit for subjects in Segment I or the Day 84 Visit for subjects in Segment II. If pre-exposure prophylactic medication for COVID-19 is administered prior to these visits the investigator should contact the sponsor-investigator to discuss if the subject should be discontinued from the study.

The sponsor-investigator must be notified in advance (or as soon as possible thereafter) of any instances in which prohibited therapies are administered. The participant should remain in the study but receive no further study vaccination.

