After data has been collected and locked as an analysis dataset, missingness will be assessed for degree as well as randomness. If the amount of missing data is small, incomplete observations will be removed from analyses of interest. On the other hand, imputation using chained equations (MICE) or random forests may be applied in the case of observations that are missing at random.

Multiplicity

There will be only a single analysis of the primary outcome across two treatment groups and therefore multiplicity is not a concern. However, for comparisons of possible confounding variables across treatment groups, multiple testing may give rise to elevated type I error. For these analyses we will consider correcting the p-values via the Benjamini-Hochberg or other methods.

Statistically significant differences on overall comparisons will be explored using multiple pairwise comparisons of each of the (n) groups using Bonferroni correction for multiple comparisons. Mean scores and standard deviation for each group will be calculated. Subsequent multiple comparisons via Tukey's procedure will be set at 0.01 to control Type I error rate.

A Note on the Incidence of COVID 19 at 2 Years

The major reason for the large numbers of patients is to have a reasonable chance of demonstrating a difference in COVID-related complications in responders vs low/non-responders after receiving the Janssen Ad26.COv2.s vaccine. The risk of COVID 19 infections in patients without anti-SARS-CoV-2 spike protein antibody is unknown and the risk of COVID infection going forward in the US also is unknown. Over the past year prior to vaccination programs, the COVID infection rate in our patient population has been approximately 10% per year with death rates of approximately 2% overall per year.

The comparisons here are one-sample comparisons of Kaplan-Meier estimates of the incidence of infection or mortality versus historical incidences of 10% and 2%, respectively.

COVID Infection Rates: Using an assumed 10% infection rate per year as the null hypothesis in the 400 patients that had an undetectable or low mRNA vaccine response, an infection rate of less than 7% will result in 90% power to demonstrate statistical significance by the one-sample log-rank test.

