COVID-Related Mortality: For mortality, a reduction from an annual rate of death due to COVID of 2% in the non-responders to 0.7% in the responders would result in 80% power to demonstrate statistical significance by the one-sample log-rank test.

Interim Analysis

No formal interim hypothesis testing will be considered and therefore alpha-spending or control of type 1 error is not of concern for this study. Data summaries will be used throughout the study to audit data quality, to create reports for the regulatory requirements (i.e.. IRB, DMSB, etc.) and to ensure the overall study is running smoothly.

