6.9 Subject Population(s) for Analysis

The subject population for the primary analysis focus on the all-completed population, i.e. the patients who had undetectable antibody levels at the time of screening and were subsequently randomized in to either maintaining immunosuppression or altering it and completed the protocol requirements for the primary endpoint (n=300 total potential patients).

Secondary analyses will be broader and focus on the all-treated population (n=400 total patients). Patients with missing data may be excluded or their data can be imputed as mentioned above. Patients who did not have complete follow-up will be censored in any survival analyses at the time of their last follow-up.

The specific study populations are:

1. All enrolled patients (up to 1200)
 - a. Up to 800 with anti-SARS-CoV-2 spike protein antibody levels ≥ 250 U/ml who will not be administered the Janssen Ad26.COVID2.S vaccine but will be followed for 2 years for outcomes including COVID-19 infection.
 - b. 400 with anti-SARS-CoV-2spike protein antibody levels < 250 U/ml who will be administered the Janssen Ad26.CoV2.S vaccine.
2. All randomized population:
 - a. n=300 to receive the Janssen Ad26.COVID2.s vaccine with 150 to receive reduced immunosuppression and 150 to maintain current immunosuppression.
3. All-treated population:
 - a. n=400.
 - b. 100 patients with low anti-SARS-CoV-2spike protein levels (>0 to <250).
 - c. 300 patients with no anti-SARS-CoV-2 spike protein levels (0).
4. All patients receiving two doses of the Janssen Ad26.CoV2.S vaccine
 - a. Up to 250 patients from the treated population who meet entry criteria for Segment II
5. Protocol compliant population:
 - a. We do not anticipate a large percentage of patients will be non-compliant with the protocol. However, the protocol is sufficiently powered to account for compliance failures.
6. All-completed populations:

- a. For the treated patient populations the most important study related procedures (received Janssen Ad26.CoV2.S vaccine and follow-up testing) will be completed within 28 days.
- b. Patients will be monitored up to 2 years post-enrollment which overlaps with the routine clinical monitoring of transplant patients at our institutions.

7 Safety and Adverse Events

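### The 2-year COVID-19 infection test has no rule for later prophylaxis or outside vaccines, so their protection can produce a significant result without any Janssen effect

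*Combined protocol and SAP*

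**What the plan says.** Section 5.6 sets a time-limited bar on prophylaxis: "Subjects should not receive any pre-exposure prophylactic medications for COVID-19 until after completion of the Day 28 Visit for subjects in Segment I", with the Day 84 visit as the corresponding point in Segment II. After that the plan permits it. The same section says "Receipt of any COVID-19 vaccine (outside the study) at any timepoint during the study must be recorded", with product name and dates in the eCRF. Under Section 7.5 an outside COVID-19 vaccine stops further study doses, but the patient stays in follow-up.

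Section 6.8 tests 2-year infection by a one-sample log-rank test, "Using an assumed 10% infection rate per year as the null hypothesis in the 400 patients that had an undetectable or low mRNA vaccine response", and states that "an infection rate of less than 7% will result in 90% power to demonstrate statistical significance by the one-sample log-rank test". For COVID death it plans for "a reduction from an annual rate of death due to COVID of 2% in the non-responders to 0.7% in the responders", which "would result in 80% power to demonstrate statistical significance by the one-sample log-rank test". Both comparators are fixed historical rates, 10% and 2% per year, from the year before vaccination programs.

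The only censoring rule is in Section 6.9: "Patients who did not have complete follow-up will be censored in any survival analyses at the time of their last follow-up". Section 6.8 also mentions Cox regression and an interest in factors related to infection at 2 years. Neither section mentions prophylaxis or outside vaccines.

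**The concern.** Incidence of COVID-19 at 2 years is a listed secondary endpoint (Section 3.5). Section 4.2 excludes patients whose earlier prophylaxis could interfere with a study endpoint, so the protocol recognises the problem at entry. The safeguard ends at Day 28 or Day 84, while infection follow-up runs about 702 days longer.

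A one-sample log-rank test has no concurrent control and takes no covariates. Anything that lowers infections after Day 28 reduces the observed count against an expected count that contains neither product. The test can then be significant when the study dose adds nothing.

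The contrast between responders and low or non-responders, which Section 6.8 gives as the main reason for the trial's size, could be biased the other way. If patients with low antibody receive more prophylaxis, a real difference would be masked.

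**Working it through.** **Inputs from the documents.** n = 400; null 10% and alternative 7% per year (Section 6.8); 2 years of follow-up after the dose (Section 3.3); two-sided 0.05 unless otherwise noted (Section 6.7); prophylaxis permitted after Day 28 or Day 84 (Section 5.6).

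**Inputs assumed.** Uptake u, efficacy e and start day are not in the documents. The calculations use exponential hazards, no dropout and protection that does not wane.

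**Test.** Z = (O − E)/√E, where O is observed infections and E is the null hazard times total time at risk. The null hazard is −ln(0.90) = 0.1054; at 7% it is −ln(0.93) = 0.0726; the ratio is 0.689.

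**The plan's own figure.** At a true 7%, O averages 400 × (1 − 0.93²) = 54.0 and E averages 54.0/0.689, about 78.5, so √E = 8.86 and √O = 7.35.
- One-sided 0.05: Φ((24.4 − 1.645 × 8.86)/7.35) = Φ(1.34) = 0.91; simulation 0.90. This reproduces the stated 90%.
- Two-sided 0.05: Φ((24.4 − 1.96 × 8.86)/7.35) = Φ(0.96) = 0.83; simulation about 0.82. Under the plan's two-sided default the power is therefore nearer 82%, a side finding.

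**Window for later protection.** In Segment I, 730 − 28 = 702 of 730 days (96%). In Segment II, follow-up runs to about Day 56 + 730 = 786, so 786 − 84 = 702 of 786 days from the first dose (89%).

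**Protection needed to reach 7% with no Janssen effect.** The average hazard must fall by 1 − 0.689 = 0.311.
- From Day 28: u × e = 0.311/(702/730) = 0.32, for example 43% × 75%.
- From Day 180: u × e = 0.311/(550/730) = 0.41.

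**One case by hand: u = 40%, e = 75%, from Day 28, no Janssen effect.**
- Unprotected patient: 2-year risk 1 − 0.9² = 0.190.
- Protected patient: cumulative hazard 0.1054 × (0.0767 + 1.9233 × 0.25) = 0.0587, so risk 0.057.
- O = 240 × 0.190 + 160 × 0.057 = 54.7.
- E per protected patient: 0.008 before Day 28 plus (0.057 − 0.008)/0.25 = 0.196 after it, about 0.204. Total E = 240 × 0.190 + 160 × 0.204, about 78.2.
- Chance that Z < −1.96: Φ((23.5 − 1.96 × 8.84)/7.40) = Φ(0.83), about 0.80.

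**Simulated chance of a significant reduction with no Janssen effect** (lower tail of two-sided 0.05; about 2% with no later protection; good to one or two points):

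| Uptake × efficacy | From Day 28 | From Day 180 |
|---|---|---|
| 20% × 75% | 26% | 16% |
| 40% × 50% | 41% | 25% |
| 40% × 75% | 80% | 52% |

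**COVID death.** The hazard ratio for 2% to 0.7% is ln(0.993)/ln(0.98) = 0.348. Producing that with no Janssen effect needs u × e of (1 − 0.348)/(702/730) = 0.68 from Day 28, or about 0.87 from Day 180. False success rises well short of that: about 21% at 40% × 75% from Day 28, taking n = 400, which Section 6.8 does not state for this test.

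**What censoring at first use does.** If uptake is unrelated to risk, false success is about 2%. If half the patients have 1.5 to 2 times the hazard of the rest, and 70% of them against 10% of the others take prophylaxis, it is about 6% to 17%. These risk and uptake figures are also assumptions.

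**The case against.** The strongest reply is that counting all follow-up is a legitimate choice. The secondary objective is to determine the incidence of infection in all enrolled patients, whether or not they received the study vaccine, and a treatment-policy analysis does that. A reader might infer that the plan will credit any reduction to the Janssen dose. No section says so, and the inference rests only on the form of the one-sample test. This stands, so the all-follow-up analysis should be kept.

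Second, a reader might take the censored analysis as the clean answer. It is not. Censoring may be informative, as shown above, and the 10% null predates vaccination programs although every patient has had at least two mRNA doses. With no Janssen effect and no prophylaxis, a true background of 9% or 8% per year gives false success of about 13–14% or 46%. Censoring removes none of that, and the historical comparator may be the larger problem.

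Third, the plan is not wholly silent. Section 6.8 has Cox models that could carry these covariates, and Section 8.5 describes registries of vaccination data. But neither product is named, and the one-sample test cannot use covariates.

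Fourth, the larger percentages assume immediate uptake and undiminished protection for nearly two years. That is fair; the Day 180 column and the smaller scenarios show how the size depends on it.

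**Conclusion.** The point holds as a cheap improvement to a secondary analysis. As written, the 2-year infection test counts time after prophylaxis or an outside vaccine in full against a rate that includes neither. Under moderate assumed use, false success rises from about 2% to between 16% and 80%. The direction follows from the documents; the size rests on uptake, efficacy and non-waning protection that they do not give.

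Three stronger readings are not supported. The Day 28 antibody endpoints are not affected, because prophylaxis is barred until that visit. For COVID death the same bias is possible, but reaching the planned reduction needs uptake × efficacy of at least 0.68. And the bias does not all favour the vaccine: the responder contrast may be pulled towards no difference.

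**What to change.** 1. Record the name and start date of any COVID-19 pre-exposure prophylaxis in the eCRF through Year 2, beside the vaccine dates already required. Include initial responders at their Year 1 and 2 reviews. Schedules 2A to 2C mark concomitant medications only to Day 28 and at unscheduled visits (Section 6.1.6 adds medication updates at Days 90 and 180), and Schedule 1 marks them only at screening.
2. In Section 6.8, keep the all-follow-up one-sample test and add a pre-specified sensitivity analysis that censors at the first prophylaxis or outside COVID-19 vaccine.
3. Enter both products as time-varying covariates in the planned Cox models.
4. State that a reduction seen only in the all-follow-up analysis will not be read as a vaccine effect, and that the censored result is not sufficient for attribution either, because the 10% and 2% rates predate vaccination.

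Cost: SAP wording and some added data collection after Day 28. The sensitivity analysis has fewer person-years. Two-sided power at a true 7% falls from about 82% to 73–76% at 20% uptake and 60–67% at 40%, and lower beyond that (about 42% at 80% uptake from Day 180). Possible informative censoring should be stated as a limitation.

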5.7 Packaging

The Janssen Ad26.CoV2.S vaccines will be packaged and labeled according to good manufacturing practices and local regulations. The Janssen Ad26.CoV2.S vaccines will not be packed in individual participant kits, 1 kit will contain 10 vials. Each vial is a single dose vial and will be used to dose only one participant.

5.8 Masking/Blinding of Study

Not applicable to this study.

5.9 Receiving, Storage, Dispensing and Return

5.9.1 Receipt of Drug Supplies

As per standard pharmacy procedures at Mayo Clinic.

5.9.2 Storage

All Janssen Ad26.CoV2.S vaccine must be stored in a secured location with no access for unauthorized personnel and at controlled temperatures as indicated on the clinical labels. If Janssen Ad26.CoV2.S vaccine is exposed to temperatures outside the specified temperature range, affected Janssen Ad26.CoV2.S vaccine must be quarantined and not used until further investigation.

Refer to IPPI/IFU for additional guidance on Janssen Ad26.CoV2.S vaccine preparation, handling, and storage.

Vials will be kept in the Mayo Clinic research pharmacy to prevent unintended or unauthorized use.

5.9.3 Dispensing of Study Drug

Regular study drug reconciliation will be performed to document drug assigned, drug dispensed, drug returns, and drug remaining. This reconciliation will be logged on the drug reconciliation form and signed and dated by the study team.

5.9.4 Return or Destruction of Study Drug

At the completion of the study, there will be a final reconciliation of drug shipped, drug dispensed, drug returns, and drug remaining. This reconciliation will be logged on the drug reconciliation form, signed and dated. Any discrepancies noted will be documented and investigated, prior destruction of unused study drug. Drug destroyed on site will be documented in the study files.

6 Study Procedures

The procedures and treatments required at each visit are outlined in the tables below, and in the following text. Any visit not described as being performed in person will be completed via telephone, telemedicine, or the Mayo Clinic portal patient communication system. Kits will be provided to the subjects so that blood samples can be shipped to the Mayo Clinic Laboratory in Rochester, MN for clinical laboratory test analysis and Mechanistic Studies for non-face to face visits. For the convenience of the participant, visits can be completed in person if they are visiting the Mayo Clinic Transplant Center during a study day window for their clinical care.

6.1 Segment I

6.1.1 Day - 21 (-30 /+7 Days)

Potential subjects will be identified by review of their medical record. If a participant is identified by review of the report, they will be contacted via the Mayo Clinic portal, the online patient communication system, phone or e-mail (if the potential subject has already contacted the study team in this manner). Study details, procedures, risks, and benefits will be described to patients interested in participation. Subjects will be consented for study participation either via telephone or at Mayo Clinic, depending on patient preference. The participant's medical history, demographics, concomitant medications and therapies, immunosuppression medications and clinical outcomes (current health and graft status) will be collected. Subjects will complete the COVID-19 Surveillance and Evaluation questionnaire (Section 14.6). Relevant medical procedures which are performed as part of the participants clinical care up to 60 days prior to signing of consent, such as clinical laboratory results may be used for determining study eligibility.

Blood for anti-SARS-CoV-2 spike protein antibody and anti-SARS-CoV-2 nucleocapsid total antibody testing will be drawn locally and sent overnight to Mayo Clinic-Rochester Laboratory for

testing. Not all screening procedures need to occur in one day. After consent is obtained, screening procedures can be completed on any day up to the baseline visit.

Patients who meet criteria will be contacted and scheduled to receive the Janssen Ad26.CoV2.S vaccine. They will be required to travel to one of the 3 Mayo Clinic transplant centers to receive the vaccine. There will be 3 groups:

1. Low-responders (n=100)
2. Non-responders (n=300)—Randomized after obtaining evidence that anti-SARS-CoV-2 spike protein antibody levels = 0 U/mL. Patients are stratified by the number of mRNA vaccines they received (2 or more).
 - a. Dosing with the Janssen Ad26.COVID-19 vaccine without immunosuppression adjustment
 - b. Dosing with the Janssen Ad26.COVID-19 vaccine with immunosuppression adjustment.

Subjects randomized to receive immunosuppression adjustment will follow one of the regimens outlined in Section 5.2.1. If randomized to the immunosuppression group, they will be contacted via phone by a physician with instruction on the participant's new immunosuppression regimen.

Adjustments will occur 2 weeks prior to receiving the Janssen Ad26.COVID-19 vaccine. In this arm, 50 patients who had T and B cell studies performed at baseline will have a second set of studies prior to receiving the Janssen Ad26.COVID-19 vaccine to determine the effect of immunosuppressive adjustment on these immune cells.

Screening study procedures can be completed at any time after consent up until the day of receiving the Janssen Ad26.COVID-19.

6.1.2 Day -14 (+/-3 Days) Non-Responder Group Immunosuppression Change ONLY

Study team will contact the subject and document their immunosuppression medication and instruct the participant to begin their new immunosuppression medication regimen. Patient and graft status information will be recorded as well as the COVID-19 surveillance information collected.

For a subset of patients randomized to receive immunosuppression adjustment: prior to the adjustment the study team will send a kit for a local blood collection for Total Immunoglobulin levels and T-/B-cell immunophenotyping. These specimens will be shipped back to Mayo Rochester via overnight courier for testing.

6.1.3 Baseline Visit (-4/+1 Day)

Subjects will return to Mayo Clinic for an in-person visit. Prior to receiving the Janssen Ad26.COVID-19 vaccine, the following study procedures will be performed:

- Serum pregnancy test for females of childbearing potential.
- Platelet count

- Mechanistic Studies
- Tacrolimus, Cyclosporine and MMF serum drug levels in subjects who are receiving these drugs or who were receiving these drugs at the time of enrollment.
- Anti-SARS-CoV-2 spike protein antibody and anti-SARS-CoV-2 nucleocapsid total antibody test
- The participant will have a nephrology consult and a complete physical exam (including review of concomitant medications and immunosuppression). The nephrologist will confirm with the IS reduction group that they have complied with their new medication regimen.
- Vital Signs (heart rate, blood pressure, temperature, pulse oximetry, height and weight).
- Asked if they are experiencing any COVID-19 symptoms or have been recently tested.

Eligible subjects will be vaccinated after these procedures have been completed. The following study procedures can be completed at any time during the visit:

- Study team will record concomitant medications and therapies.
- Study team will document immunosuppression medication
- Patient Status and Graft Status
- Risk Factor Assessment (see Section 14.5)
- Safety Follow Up Questionnaires (questions related to potential GBS, TTS, myocarditis and pericarditis symptoms)
- Kidney Transplant Follow-Up Questionnaire

To differentiate symptoms potentially related to the Janssen Ad26.COV2.S vaccine, the participant will be asked about any symptoms they may currently be experiencing prior to vaccination as well as after to differentiate potential vaccine related adverse events. Then they will receive the Janssen Ad26.COV2.S vaccine during a clinical appointment. All vaccination will be monitored post vaccine for 30 minutes for potential reactions to the vaccination.

